10.3.4 Definition of ST3P UP Application Usage

- Usage will be documented in two ways for each study subject (EA-SCD, mentor, and advisor):
 - o Frequency of contacts between subjects and transition coordinator
 - o Frequency of educational resource views
- Usage will also be documented on the investigator and transition coordinator level, as frequency of contacts between investigator and transition coordinator and contacts between investigators across sites within the project.

10.3.5 Definition of Site-Level Endpoints

Health Care Transition Feedback Survey for providers:

• Provider satisfaction with transition services will be collected using a standard 5-point Likert scale.

Health Care Transition Process Measurement Tools:

- For Transitioning Youth to Adult Healthcare Providers (pediatric clinics)
- For Integrating Young Adults to Adult Healthcare Providers (adult clinics)

These elements of healthcare transition will be captured longitudinally for each site and will consist of the Core Elements of Health Care Transition. Scores will be self-reported by sites and then confirmed by the QI Coordinator. All Core Elements scores will be a

weighted sum of the individual items, and the overall HCT score will be a sum of the Six Core Element scores.

10.4 Analysis Populations

All EA-SCD participant-level analyses will be conducted on the population of all enrolled EA-SCD participants (consented EA-SCD participants who are enrolled per section 10.1.2), regardless of how long the EA-SCD participant was on study or regardless of the extent of data missingness.

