STATISTICAL CONSIDERATIONS	Estimated average acute care utilization rate for EA-SCD is 6 visits / year. This study is designed to detect a 20% reduction in the number of acute care encounters per year which is considered clinically significant to our patient stakeholders. Based on a two- sided alpha = 0.05 significance level, 67 subjects per arm would provide approximately 85% power to detect a 20% reduction in the number of acute care utilizations under individual randomization, assuming the number of encounters follows a Poisson distribution for rare events. Sample size was inflated based on the cluster size coefficient of variation among our 14 participating clinical sites (55%) and the intra-class correlation (ICC) assumed to be 0.05. Based on these parameters, 183 subjects per arm (366 total subjects) will retain approximately 85% power. The sample size was increased to 537 total EA-SCD subjects to account for potential missing data and allow for robust evaluation of secondary endpoints. It is estimated that this can be accomplished with an enrollment rate of 35% of the EA-SCD patient population.
NUMBER OF EA-SCD PARTICIPANTS	537 total participants will be enrolled Each arm will enroll approximately 269 EA-SCD aged 16 – 25 years
NUMBER OF CLUSTERS	There will be 14 cluster sites, each cluster site comprised of a pediatric SCD clinic, an adult SCD clinic and a SCD CBO. There are 8 large cluster sites with ≥40 EA-SCD currently in pediatrics and 6 small cluster sites with <40 EA-SCD currently in pediatric care. Based on self-reported enrollment targets from each site, 80% of participants will come from large clusters.

SCHEMA

[figure not shown]
Study Schema Figure 1: Overview of Study Design

	Study Schema										
Practices with Emerging Adults with SCD (EA-SCD) aged 16 - 25y Randomized at the Practice Level											
Small Sized Program [≤ 40 EA-SCD] Large Sized Program [> 40 EA-SCD]											
Arm 1- A	Arm 1- B	Arm 2-A	Arm 2-B								
Structured Education Based Transition Program [STE]	Structured Education Based Transition Program [STE] + Peer Mentoring [STE + PM]	Structured Education Based Transition Program [STE]	Structured Education Based Transition Program [STE] + Peer Mentoring [STE + PM]								
	Outcome Meas	ures at 24 Montl	ns								
Primary Outcome: Cha		are visits [ED visits, Adm Hospital Days]	issions, Readmissions at 14d,								

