10.2 Sample Size and Accrual

Sample size calculations are based on the primary endpoint of acute care utilization visits per year (at the EA-SCD participant level). Utilizing a randomized cluster design, seven clinical sites will be randomized per arm. The sample size calculation strategy is to calculate the required minimum sample size based on an individual patient randomized design, and then inflate the sample size based on cluster randomized considerations.⁵⁴ A conservative estimate of the average acute care utilization rate for EA-SCD is 6 acute care visits per year based on data for North Carolina reported by the RuSH population surveillance project.⁴ In South Carolina, the acute care utilization rates among 18-30 y with SCD was reported as 7.17 (95% CI 6.34-7.99).55 At Atrium Health (formerly known as Carolinas Healthcare System), 295 EA-SCD had 1972 emergency department visits and 221 hospital admissions in 2015 with an average acute care

utilization rate of 6.82 visits per year. This study is designed to detect a 20% reduction in the number of acute care encounters per year (assuming a base case of 6 encounters). A 20% reduction in acute care utilization is considered clinically significant based on patient partners reporting that 1 less acute care visit a year is meaningful. Based on a two- sided alpha = 0.05significance level, 67 EA-SCD participants per arm would provide approximately 85% power to detect a 20% reduction in the number of acute care utilizations under individual randomization, assuming the number of encounters follows a Poisson distribution for rare events. The sample size will be inflated based on two parameters: the cluster size coefficient of variation and the intra-class correlation (ICC).⁵⁴ The cluster size coefficient of variation observed among the 14 participating clinical sites is 55%. Therefore, the coefficient of variation is assumed to be 60% and the ICC is assumed to be 0.05.⁵⁶ Based on these parameters, a minimum of 183 EA-SCD participants per arm (366 total EA-SCD participants) will retain approximately 85% power. To account for potential missing data and allow for robust evaluation of secondary endpoints the sample size will be increased to a total of 537 EA-SCD participants. It is estimated that this enrollment can be accomplished with an enrollment rate of 35% of the EA-SCD patient population.

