10.3 Endpoints

10.3.1 Definition of Primary Endpoint

Acute care visits will be calculated for each EA-SCD participant as the average number of acute care visits over a24-month period. Acute care visits will also be calculated for each EA-SCD participant as the average number of acute care visits per year over the entire study as a secondary endpoint. Acute care visits may include, but are not limited to hospital admissions, ED, urgent care, day hospital, or infusion center visits. The calculations for these endpoints are below:

$$Months \ on \ study = \frac{(Off \ Study \ Date - Enrollment \ Date)}{30.4375}$$

$$Acute \ care \ visits \ per \ 24 \ months = \frac{Total \ \# \ acute \ care \ visits \ reported \ on \ study}{Months \ on \ study} * 24 \ months$$

$$Acute \ care \ visits \ per \ 12 \ months = \frac{Total \ \# \ acute \ care \ visits \ reported \ on \ study}{Months \ on \ study} * 12 \ months$$

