10.3.2 Definition of Secondary Endpoint

Quantitative EA-SCD participant-reported outcome scores will be captured longitudinally for each subject. Data will be collected for each subject using the following scales:

- Adults Sickle Cell QOC Measure (ASCQ-ME QOC) for health-related quality of life
- PedsQLTM-SCD module for health-related quality of life
- Medical Outcomes Study Social Support Survey (MOS-SSS)
- Transition Readiness Score as measured by the TIP-RFT scale
- Health Care Transition Feedback Survey

Count variables capturing healthcare utilization will be calculated for each EA-SCD participant for the following variables. These will be annualized to 12-month and 24-month periods as described above.

- The number of ambulatory visits
- The number of visits with adult providers
- The number of hospitalization days
- 14-day and 30-day readmission rates

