10.5.4 Primary Analysis

To evaluate the impact of PM, the acute care utilization rate per year will be compared between the PM+STE and STE arms. This will be accomplished using generalized linear mixed model with a Poisson distribution-log link construct. The model will include fixed effects for baseline acute care visits per year, the stratification factor (large sites vs small sites) and treatment arm, and a random effect for clinical site. Corresponding 95% confidence intervals will be calculated for the estimated ACU rate in each treatment arm.

Supportive and sensitivity analyses will be conducted to include potential confounding factors such as urban versus rural sites, education level, older first degree relative with SCD, genotype, age at transfer to adult care, and type of receiving provider (primary versus specialty). Univariate models will be fit for each factor, and those identified to be individually prognostic will be included in a multivariable model, and backward elimination followed by forward selection will be used to identify factors that are independently prognostic and to establish a final base model. Finally, treatment arm will be added to the base model to evaluate the impact of the intervention adjusting for significant baseline factors.

Two analyses will be conducted to estimate the impact of differential accrual between arms over time: (1) An additional term of year of enrollment will be added to the GLMM as a categorical variable; (2) We will subset the analyses to EA-SCD who were contemporaneously enrolled. Comparison of the PM+STE and STE ACU estimates from this subset to those results including all enrolled with and without controlling for year of enrollment will provide a comprehensive assessment of the potential bias due to differential accrual between arms over time. ACU rate in the STE only arm will be compared to historical ACU rates which were used for the original power calculations. Although these are comparisons to historical controls, this will provide preliminary evidence using a robust sample size of the potential impact of the structure transition education.

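### Acute care visits are rescaled to 12 or 24 months for a Poisson model with no exposure offset specified; the visit count with log(months observed) as offset should be the response.

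*Combined protocol and SAP*

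**What the plan says.** Section 10.3.1 defines months on study from the enrollment and off-study dates, divides total visits by it, and multiplies by 24 for the primary endpoint. The version multiplied by 12 is secondary: "Acute care visits will also be calculated for each EA-SCD participant as the average number of acute care visits per year over the entire study". Section 10.3.2 extends this to ambulatory visits, adult-provider visits, hospital days and readmissions: "These will be annualized to 12-month and 24-month periods as described above".

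Section 10.5.4 compares the yearly rate between arms with a Poisson, log-link generalized linear mixed model: "The model will include fixed effects for baseline acute care visits per year, the stratification factor (large sites vs small sites) and treatment arm", plus a random site effect. The other utilization outcomes are handled similarly. No offset, exposure term or follow-up weight is mentioned there or elsewhere.

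Section 10.4 analyses all enrolled participants, "regardless of how long the EA-SCD participant was on study or regardless of the extent of data missingness". Section 7.1 stops data collection once a participant is off study, so early leavers have short exposure. Section 10.5.6 deals with missing covariates and patient-reported outcomes, not with unequal follow-up for utilization. Section 2.1 words the objective as visits per year over 24 months, which does not settle the scale.

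**The concern.** A Poisson likelihood reads its response as a number of events actually seen, with variance equal to the mean. A rate that has already been divided by time and multiplied by 12 or 24 is not such a number. Four things follow if it is used as the response.

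- **Weights.** Someone followed for one month counts as much as someone followed for 30. Short, noisy records are magnified, and completers beyond 24 months are scaled down, which discards information.
- **Non-counts.** The response is generally not an integer.
- **Zero exposure.** The value is undefined when the off-study and enrollment dates coincide, yet 10.4 includes that person.
- **Scale.** Multiplying by 24 rather than 12 tells the model that it has twice as many events, from the same data. Section 10.3.1 makes the 24-month value primary; 10.5.4 analyses per year.

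The primary analysis and the other utilization models are affected. The interim analysis is exposed too: its median follow-up is put at about 11 months (10.5.9), so many participants would be scaled up.

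**Working it through.** **The plan's own figures.** Section 10.2 gives "assuming a base case of 6 encounters" per year, a 20% reduction (to 4.8), two-sided alpha 0.05 and "67 EA-SCD participants per arm would provide approximately 85% power". Under Poisson, n = (1.960 + 1.036)² × (6 + 4.8) / 1.2² = 67.3. With 7 sites per arm, ICC 0.05 and cluster-size CV 0.60, n = 67 × 0.95 / (1 − 67 × 0.05 × 1.36 / 7) = 182.3, rounded up to 183. Both figures reproduce and are unaffected by this point.

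**One participant.** Two visits in 1 month: 2 / 1 × 12 = 24, or 2 / 1 × 24 = 48.

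**Scale, Poisson part only.** SE of the log rate ratio = √[1/(183 × 6 × s) + 1/(183 × 4.8 × s)], with s in years. This gives 0.0453 for s = 1 and 0.0320 for s = 2, a ratio of √2 from identical data. If all had 30 months and the real counts were used, it would be 0.0286.

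**Cost of equal weighting, Poisson visits, no site effect.** The mean of individual rates has variance proportional to E[1/T]; total visits over total time has variance proportional to 1/E[T]. The ratio is E[T] × E[1/T]. The plan states no dropout rate, so two patterns are assumed, each with 30% leaving early:

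- Pattern A: leavers uniform over 1–24 months, others 30 months. E[T] = 0.7 × 30 + 0.3 × 12.5 = 24.75; E[1/T] = 0.7/30 + 0.3 × ln(24)/23 = 0.0648; ratio 1.60. At 10%, 20% and 50% leaving: 1.24, 1.44 and 1.82.
- Pattern B: leavers uniform over 0.5–18 months, others 24–36. E[T] = 0.7 × 30 + 0.3 × 9.25 = 23.78; E[1/T] = 0.7 × ln(1.5)/12 + 0.3 × ln(36)/17.5 = 0.0851; ratio 2.02.

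**In the planned mixed model.** I simulated 14 sites and 536 participants with no treatment effect, 1,000 trials per row, and fitted a Poisson model with a random site intercept by adaptive quadrature (arm and site size as fixed effects; baseline visits omitted). The rate was 6/year for A and 4/year for B. Two inputs come from the protocol:

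- Site CV: ICC 0.05 at a rate of 6 gives √(0.05/0.95 × 6) / 6 = 0.094.
- Person-level variance: the mean of 5.3 and SD of 8.5 in section 1.1 give (8.5² − 5.3) / 5.3² ≈ 2.4 (gamma).

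| Setting | Variance vs offset: ×12, ×24 | Null rejection: ×12 / ×24 / offset | Median SE, ×24 ÷ ×12 |
|---|---|---|---|
| A, no site variation | 1.56, 1.63 | 2% / 7% / 5% | 0.75 |
| B, no site variation | 1.95, 2.10 | 5% / 10% / 4% | 0.85 |
| A, site CV 0.094 | 1.18, 1.15 | 10% / 10% / 10% | 0.99 |
| B, site CV 0.094 | 1.27, 1.25 | 11% / 11% / 11% | 0.99 |
| A, person variance 2.4 | 0.84, 0.90 | 11% / 11% / 11% | 1.02 |
| B, person variance 2.4 | 0.80, 0.87 | 9% / 10% / 11% | 1.03 |

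Monte Carlo error on the rejection rates is up to about 1 percentage point. Midway between A and B with no site variation, the variance ratio is (1.56 + 1.95)/2 = 1.76 for ×12 and (1.63 + 2.10)/2 = 1.87 for ×24.

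**The case against.** **The plan does not exclude an offset.** Section 10.5.4 lists fixed and random effects, and an offset is neither. A rate compared in a log-link Poisson model usually has one, and 10.3.2 calls the utilization variables counts. This stands: the accurate statement is that no offset is specified, and that the scaled value is the response is an inference from reading 10.3.1 and 10.5.4 together. It does not rescue the text. The endpoint is already divided by time, so adding an offset to it would adjust for time twice.

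**The random site effect absorbs most of the scale problem.** A reader might infer that the standard error always moves by √2, or that the p-value is routinely driven by the choice of scale. The table does not support that. The full √2 needs an estimated site variance of zero; at the plan's ICC the two standard errors differ by about 1%. The roughly 10% rejection at site CV 0.094 is shared by all three analyses, so it cannot be charged to the scaling.

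**The precision gain depends on Poisson visits.** Section 1.1 reports SDs above the means in every age band. With variation of that size the offset estimate is no more precise, and somewhat less so in these runs. This also stands.

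**Inputs are assumed.** Early-leaving rates and times are not in the documents, and pattern B's 24-month completers fall short of the planned 30 months or more. Zero-month cases will be rare, since withdrawals before enrollment are screen failures (3.6). The population rule in 10.4 is itself sound and need not change.

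**Conclusion.** The point holds as a defect of specification in the primary analysis. Sections 10.3.1 and 10.5.4, read with 10.4, lead to a Poisson model of scaled non-counts that ignores length of follow-up and rests on an unresolved scale.

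Under the Poisson assumption of section 10.2 and 30% assumed early leaving, the variance of the log rate ratio is about 1.8 to 1.9 times that of the offset analysis with no site variation (1.6 to 2.1 across the two patterns), and about 1.2 to 1.3 times at site CV 0.094. Excess false positives specific to the 24-month scale (7% to 10%) appear only when sites do not vary.

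Two stronger conclusions are not supported. One is that every utilization standard error will be badly wrong because of the scaling. The other is that an offset would make the Poisson variance adequate: with strong person-level variation it neither gains precision nor corrects overdispersion. Nor does it remove bias if withdrawal is related to illness. The case for it is that it uses real counts, weights by actual exposure and removes the dependence on scale at almost no cost.

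**What to change.** Before the final analysis:

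- **10.5.4:** state that the response is the integer number of visits (or hospital days) with log(months observed) as offset, in whatever count model is finally used, for the primary and the other count-type utilization endpoints.
- **10.3.1 and 10.3.2:** keep the scaled rates for descriptive tables only.
- **Scale:** reconcile the 24-month primary endpoint with the yearly comparison in 10.5.4, and say which follow-up window supplies the counts. With an offset, the reporting unit then no longer affects inference.
- **Zero exposure:** state that participants with no observed time stay in the population of 10.4 but contribute no information to these models.
- **Readmissions:** give the 14-day and 30-day measures a suitable denominator, such as discharges, rather than months on study.

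The cost is a few sentences. Visits and the dates that define exposure are already collected, so no new data are needed, participants carry no extra burden, and the sample size does not change. Overdispersion needs its own provision in the choice of count model.

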10.5 Analysis Methods

10.5.1 Timing of Analysis

Study outcomes will be evaluated on an ongoing basis to monitor enrollment, derivation of study endpoints, assessment of missingness, and attrition. Additionally, the cluster size coefficient of variation and ICC will be evaluated on an ongoing basis to assess design assumptions.

A planned interim analysis will be performed as described in Section 10.5.8. A final analysis will be conducted after all EA-SCD participants are off study.

10.5.2 Subject Disposition

EA-SCD participant disposition will be provided in terms of a CONSORT diagram with an extension to cluster randomized trials. This will include all EA-SCDs consented, those initiating transition, and EA-SCD withdrawals. Reasons for EA-SCD withdrawals will be provided as well as a summary of the number of and reasons for missing data for key outcome measures.

10.5.3 Baseline Subject Characteristics

A summary of EA-SCD participant demographics, disease characteristics, and acute/ambulatory care utilization in the 12 months prior to enrollment will be assessed.

A summary of mentor/advisor demographics and disease characteristics will also be completed.

10.5.4 Primary Analysis

To evaluate the impact of PM, the acute care utilization rate per year will be compared between the PM+STE and STE arms. This will be accomplished using generalized linear mixed model with a Poisson distribution-log link construct. The model will include fixed effects for baseline acute care visits per year, the stratification factor (large sites vs small sites) and treatment arm, and a random effect for clinical site. Corresponding 95% confidence intervals will be calculated for the estimated ACU rate in each treatment arm.

Supportive and sensitivity analyses will be conducted to include potential confounding factors such as urban versus rural sites, education level, older first degree relative with SCD, genotype, age at transfer to adult care, and type of receiving provider (primary versus specialty). Univariate models will be fit for each factor, and those identified to be individually prognostic will be included in a multivariable model, and backward elimination followed by forward selection will be used to identify factors that are independently prognostic and to establish a final base model. Finally, treatment arm will be added to the base model to evaluate the impact of the intervention adjusting for significant baseline factors.

Two analyses will be conducted to estimate the impact of differential accrual between arms over time: (1) An additional term of year of enrollment will be added to the GLMM as a categorical variable; (2) We will subset the analyses to EA-SCD who were contemporaneously enrolled. Comparison of the PM+STE and STE ACU estimates from this subset to those results including all enrolled with and without controlling for year of enrollment will provide a comprehensive assessment of the potential bias due to differential accrual between arms over time. ACU rate in the STE only arm will be compared to historical ACU rates which were used for the original power calculations. Although these are comparisons to historical controls, this will provide preliminary evidence using a robust sample size of the potential impact of the structure transition education.

An additional sensitivity analysis will be conducted to assess the impact of the cluster of mentees/patients within mentors for the intervention arm. We will analyze the data using the recommended heteroscedastic partially nested mixed effects model (Candlish et al BMC Medical Research Methodology 2018 18:105) and compare the results to the primary analysis which only adjusts for the clustering within site.

Additionally, the number of ambulatory visits, the number of visits with adult providers, hospitalizations, and readmissions will be analyzed in a similar fashion as described above. An acute care reliance measure will be estimated based on the model-based estimates of **Acute Care Visits / [Acute Care Visits + Ambulatory visits].**

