specialized and primary - during transition, amplifying existing barriers to accessing crucial services as disease burden is increasing. 20,21 A retrospective study showed that patients who are transitioning received 46% fewer transfusions by age 22y compared to children and were 4.7 times less likely to receive iron chelation by age 25y. 21 At Atrium Health (formerly known as Carolinas Healthcare System), a large healthcare system in the SE US that provides care for 1300 adults and 400 children with SCD, only 8-14% of EA-SCD accessed a scheduled visit with their primary care/SCD provider in 2015 with mean acute care reliance (ACR; number of acute care visits per year/ [all acute care visits + all ambulatory care visits]) rates of 42% (Fig 2). Mean acute care visits/year rose significantly from 2.1 ± 2.9 among 16- 18y to 4.2 ± 6.8 among 19 - 21y and was highest among 21 - 25y at 5.3 ± 8.5 (p<0.01). ACR (\geq 0.33) is an indicator of inadequate access to primary and preventative care. 22 EA-SCD report having inadequate information about adult care and a poor understanding of their disease and how it becomes more complex with age. $^{14, 16}$ There are significant knowledge gaps and poor communication between pediatric and adult providers that worsen the problem created by a lack of standardized EA-SCD patient education curriculum.

Limited evidence on effective transition programming:

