ST3P UP application usage will be analyzed descriptively in terms of number of contacts between study subjects and transition coordinators, transition coordinators and PIs, and between PIs. Additionally, the use of education resources in the application will be summarized descriptively for the study subjects. Associations between EA-SCD outcomes (particularly acute care utilizations) and contact frequency, will be analyzed similarly to the methods described above for the primary analysis, with treating the app usage as a continuous covariate. Additionally, application usage will be correlated with EA-SCD PROs (specifically TIP-RFT assessments) similarly to the methods described above, treating the app usage as a continuous covariate. For the analysis described about regarding application usage, this will be done in two ways: (1) including all subjects and, for subjects who did not use the application, usage would be equal to zero; (2) only including the subset of subjects who used the application and looking at the impact of amount of usage on outcomes.

Composite QI-validated scores of the Six Core Elements provided by the sites in 6-month intervals will be analyzed using linear mixed models for repeated measures. One goal of the QI analyses is to assess the convergence in scores between pediatric and adult practices. This will be accomplished with a model that includes baseline QI score, clinic (pediatric versus adult), time, and the provider by time interaction as fixed factors. Site will be included as a random factor to account for repeated observations over time. Importantly, the type of provider will also be evaluated. This will be accomplished using a similar model as described above but will use provider type: Pediatrician to Pediatrician; Pediatrician to Internist; Pediatrician to Med/Peds Specialist, Med/Peds specialist to Med Peds specialist as the treatment factor. Additionally, composite QI-validated scores will be compared with site self-reported scores for concordance over time. Provider satisfaction with transition services will be summarized descriptively.

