10.5.7 Exploratory Analysis

Heterogeneity of Treatment Effects: We will evaluate the consistency of the intervention across site and patient level characteristics. The heterogeneity of treatment effects (HTE) will be evaluated using potential treatment effect modifiers measured prior to randomization. Site level factors will include cluster size (large vs small) and urban vs rural sites, while subject level factors are those previously listed in the multivariable modeling description. For each factor, subgroup analysis will be conducted on each of the mutually exclusive factor levels. Evaluation of the HTE will be performed qualitatively by comparing the treatment group differences across the factor levels. More formally, each subject-level factor will be evaluated using models to include treatment arm, the baseline factor, and the treatment by factor interaction.

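### The Poisson count models have only a site random effect: subject-level tests ignore differences between persons, and the arm test has no small-sample method for 14 sites

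*Combined protocol and SAP*

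**What the plan says.** Section 10.5.4 sets the primary model as a "generalized linear mixed model with a Poisson distribution-log link construct". Its terms are baseline visits, the site-size stratum, "treatment arm, and a random effect for clinical site". The same section later describes the primary analysis as adjusting for site clustering alone.

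The approach is reused:

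- **Covariate screening (10.5.4):** single-factor models are fitted, and "those identified to be individually prognostic will be included in a multivariable model", followed by backward and forward selection. Year of enrollment is also added to this model.
- **Other counts (10.5.4):** ambulatory visits, adult-provider visits, "hospitalizations, and readmissions will be analyzed in a similar fashion as described above".
- **App usage (10.5.5):** associations of outcomes with "contact frequency, will be analyzed similarly to the methods described above for the primary analysis".
- **Effect modifiers (10.5.7):** "models to include treatment arm, the baseline factor, and the treatment by factor interaction". The model family is not named here.

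For the counts the plan states no participant random effect, negative-binomial or quasi-Poisson form, dispersion check, robust variance, estimation method, degrees of freedom or few-cluster correction. Section 10.5.5 does include a subject-within-site factor in the patient-reported outcome models. The partially nested model in 10.5.4 is a sensitivity analysis for clustering by mentor in one arm and is not a person-level dispersion term.

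On the data, Section 1.1 gives visits per year of 2.1 ± 2.9 (16-18y), 4.2 ± 6.8 (19-21y) and "highest among 21 - 25y at 5.3 ± 8.5". On the design, Section 10.2 says "seven clinical sites will be randomized per arm".

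**The concern.** There are two separate faults.

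1. **Subject-level tests.** A Poisson model with a site intercept has no term for differences between persons within a site beyond what baseline visits explain. If counts vary between persons as Section 1.1 reports, standard errors for person-level covariates are too small. Noise factors would be labelled prognostic and enter the adjusted base model, and app-usage and effect-modifier results would look far more certain than they are.
2. **Arm test.** Arm varies only between sites, so the comparison rests on 14 units. A large-sample z test with maximum-likelihood standard errors is too liberal at that number, and the plan does not rule it out. This fault is present with no overdispersion at all, so a dispersion term alone does not cure it.

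**Working it through.** **The plan's own figure.** Section 10.2 assumes Poisson counts, 6 versus 4.8 visits per year, two-sided 5% and 85% power.

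- Individual randomization: n = (1.960 + 1.036)² × (6 + 4.8) / 1.2² = 67.3, against 67 stated.
- Cluster inflation with k = 7, ICC 0.05, CV 0.60: m = 67 × 0.95 / (7 − 67 × 0.05 × 1.36) = 26.04 per site, so 7m = 182.3, against 183 stated.

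The figures reproduce, with variance equal to the mean built into the first step.

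**Dispersion in Section 1.1**, where κ = (variance − mean)/mean²:

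| Age | Variance/mean | κ |
|---|---|---|
| 16-18y | 2.9²/2.1 = 4.0 | 1.43 |
| 19-21y | 6.8²/4.2 = 11.0 | 2.38 |
| 21-25y | 8.5²/5.3 = 13.6 | 2.38 |

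**Analytic check without baseline adjustment.** A nominal 5% test rejects with probability P(|Z| > 1.96/√φ), where φ is the variance/mean ratio. For one year this gives 33% (φ = 4.0) to about 60% (φ = 13.6). For two years at 5.3 ± 8.5, φ = 1 + 2.38 × 10.6 = 26.2, which gives about 70%.

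**Null simulation with baseline adjustment.** Inputs from the documents: 14 sites, 537 participants, 80% of them in 8 large sites, cluster-size CV 0.60, and the two constrained health systems placed in the same arm. Assumed: baseline correlation 0.5-0.9, baseline on raw or log scale, site log-SD 0.2 (0.1 and 0.36 at zero dispersion), equal follow-up of 1 or 2 years. There were 1,000 trials per scenario (Monte Carlo error about 1.4 points at 5%).

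| κ | Subject-level null rejection |
|---|---|
| 0 | 5-6% |
| 0.5 | 25% |
| 1.43 | 19-46% |
| 2.38 (21-25y figures) | 37-69% |

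At the plan's minimum of 366 participants the last two rows gave 28-30% and 54-57%. With lognormal instead of gamma variation between persons they gave 26-30% and 56-58%. Residual variance/mean after baseline and site was 2.2-6.0 (κ = 1.43) and 3.9-20.9 (κ = 2.38). Putting these into the analytic formula gives 19-42% and 32-67%, close to the simulated ranges. A second simulation set (2,500 trials per scenario) gave about 18-71%, and 5% with pure Poisson data, so overdispersion is the cause.

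**Break-even.** Rejection stays under 10% only if φ < (1.96/1.645)² = 1.42. Baseline adjustment would have to remove 1 − 0.42/3.0 = 86%, 1 − 0.42/10.0 = 96% and 1 − 0.42/12.6 = 97% of the excess in the three age groups.

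**Arm test.** Degrees of freedom: 14 sites − 3 site-level fixed effects (intercept, stratum, arm) = 11.

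| Method | Overall | At zero overdispersion |
|---|---|---|
| ML, Wald z | 9-13% | 12% |
| REML-type, z | 6-9% | 8-9% |
| ML, t(11) | 6-9% | 9% |
| REML-type, t(11) | 4-6% | 6% |

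An ICC of 0.05 at a mean of 6 corresponds to site log-SD σ with 36σ²/(36σ² + 6) = 0.05, so σ = 0.094. In the second set, pure Poisson data at that value gave 12.4-13.0% with ML and z. The inflation vanished (4.4%) only when sites did not vary, which contradicts the plan's ICC.

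**The case against.** The strongest points on the other side are these.

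- **The 20-70% does not touch the primary comparison.** This is correct. The site variance absorbs person-level dispersion in the arm test, and the affected tests are supportive or exploratory. Section 10.5.7 looks at effect modifiers qualitatively first and names no model.
- **Noise covariates barely move the arm result.** This stands. A simulation with five null binary covariates (250 trials per scenario) kept 27% and 50% of them at the lowest and highest Section 1.1 dispersions. The arm test moved only from 8.8% to 9.2% and from 8.8% to 10.0%, within Monte Carlo error of about 3.6 points. The harm is false labelling of factors, and it presumes a 5% screening threshold that the plan does not state.
- **The arm fault is silence.** This is true: 9-13% needs ML with Wald z, which the plan neither specifies nor excludes. The error ranges over 4-13% with a choice left open.
- **The upper end depends on assumptions.** Modelling annualized rates, as Section 10.3.1 may imply, would bring dispersion close to the one-year values (unadjusted maximum about 60% instead of 70%). With a baseline correlation of 0.95 the range is 18-39%, still well above 5%.
- **The Section 1.1 figures may not describe this endpoint.** They are marginal figures from one health system. Section 10.2 gives 6.82 visits per year for the same system, which no weighted average of 2.1, 4.2 and 5.3 can reach, so definitions or samples differ. This lowers confidence in the exact range. The 86-97% break-even shows how far the data would have to differ.
- **The synopsis says the peer-mentoring comparator cannot be assessed quantitatively as first planned.** That reduces the weight of the arm test, but Section 10.5.4 still specifies it, and the screening and app-usage analyses do not depend on the arm contrast.

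**Conclusion.** The concern holds on both counts and should be fixed. At the dispersion the protocol itself reports, subject-level tests from the stated model reject a true null about 20-70% of the time at nominal 5%. The exact figure depends on baseline correlation, baseline coding, follow-up length and whether the Section 1.1 spread carries over to enrolled participants; residual dispersion after adjustment is not given. The consequence is confined to supportive, secondary and exploratory findings. For the primary comparison, the stated 5% is not secured: one permissible reading of the plan about doubles it, while another keeps it at 4-6%.

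**What to change.** Amend Sections 10.5.4, 10.5.5 and 10.5.7 as follows.

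1. **Counts.** For every utilization count, use a negative-binomial mixed model or add a participant-level random intercept to the Poisson model, and name the model in 10.5.7. In simulation (500 trials per scenario, Monte Carlo error about 1.9 points) the negative-binomial form brought subject-level rejection to 5.0-8.0% with gamma and 7.4-9.0% with lognormal variation between persons.
2. **Robust check.** Because that is still somewhat liberal, report subject-level terms with participant-level robust standard errors as well (3.0-7.0% in the same simulations). State how the sandwich estimator is formed alongside the site random effect.
3. **Arm test.** Specify REML-type estimation with small-sample degrees of freedom based on sites (about 11, or Kenward-Roger). With the negative-binomial model this gave 3.2-5.6%, against 7.0-10.6% with ML and z.
4. **Permutation check.** Add a stratified site-level permutation test that respects the same-arm constraint in Section 4.2. Assuming splits of 4/4 and 3/3 and one site per constrained system, C(8,4) × C(6,3) = 1,400 allocations reduce to 600 (both large), 700 (one of each) or 560 (both small). The smallest two-sided p is 2/700 to 2/560, about 0.003-0.004.

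The cost is SAP wording and a different model call; no new data are needed. The arm interval widens by 2.20/1.96, about 12%, plus the REML effect. Moving from z to t(11) takes a nominal 85% power to about 79% (2.996 − 2.201 = 0.795, Φ = 0.787). Subject-level standard errors grow by roughly the square root of the residual variance/mean, which is 1.5-fold at 2.2 and 4.6-fold at 20.9.
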